## 6.15. Protocol Violations

Protocol deviations will be tracked by the clinical team and their importance will be assessed by key team members during protocol deviation review meetings. All important protocol deviations (IPDs) identified with the potential to affect efficacy analyses will result in exclusion from the PPS population.

Potential examples of deviations include patients who receive excluded concomitant therapy, significant noncompliance with study medication (<80% of assigned doses taken, failure to take study medication, and taking incorrect study medication), patients incorrectly enrolled in the study, and patients whose data are questionable due to significant site quality or compliance issues. Refer to a separate document for the important protocol deviations.

Trial Issue Management Plan includes the categories and subcategories of IPDs and whether or not these deviations will result in the exclusion of patients from per protocol set.

The number and percentage of patients having IPD(s) will be summarized within category and subcategory of deviation by treatment group using the ITT population. Individual patient listings of IPDs will be provided. A summary of reasons patients were excluded from the PPS population will be provided by treatment group.

## 6.16. Interim Analyses and Data Monitoring

A Data Monitoring Committee (DMC) will oversee the conduct of this trial. The DMC will consist of members external to Lilly. This DMC will follow the rules defined in the DMC Charter, focusing on potential and identified risks for this molecule and for this class of compounds. The DMC will include at least 2 physicians with experience as a DMC member and/or clinical trial experience with a specialty in acute care, pulmonary medicine, or infectious diseases, as well as a biostatistician with DMC and clinical trial experience.

The DMC will be authorized to review unblinded results of analyses by treatment group prior to the final database lock, including, but not limited to, study discontinuation data, AEs including serious adverse events (SAEs), selective clinical laboratory data, and vital sign data. The DMC may recommend continuation of the study, as designed; modify study protocol as specified; temporary suspension of enrollment; the discontinuation of the entire study; or recommend increasing the sample size. Details of the DMC, including its operating characteristics are documented in the Data Monitoring Committee Charter for Phase 3 Study of Baricitinib in COVID-19 Program and further details are given in Section 6.16.1 of the Interim Analysis Plan.

### 6.16.1. Interim Analysis Plan

The following are the planned interim analyses for the KHAA Phase 3 study:

- interim analysis: for futility and safety monitoring, unblinded, selective efficacy/safety data will be reviewed, and
- safety and mortality review: for safety and mortality monitoring purposes only, unblinded mortality data and selective safety data will be reviewed.

- Sample size re-estimation (SSR): results of an interim analysis for the purposes of sample size re-estimation will be reviewed. Criteria will be provided, and the DMC may recommend increasing the sample size if the criteria for increase are met.

Additional details of interim analyses are summarized in the DMC charter.

The primary endpoint for the interim analysis for futility is:

- proportion of patients that require noninvasive ventilation/high-flow oxygen or invasive mechanical ventilation (including ECMO) or die by Day 28.

The interim futility analysis methods are described in detail in the DMC charter. Beside the futility interim analysis, the DMC will also review safety data as specified in the DMC charter provide their recommendation for SSR. The details of SSR are provided in Section 6.16.2.

Summaries will include TEAEs, SAEs, special topic AEs, and treatment-emergent high and low laboratory and vital signs in terms of counts, percentages, and incidence rates (IRs), where applicable. For continuous analyses, box plots of laboratory analytes will be provided by time point and summaries will include descriptive statistics.

For interim futility review, the summary of proportion of patients that require noninvasive ventilation/high-flow oxygen or invasive mechanical ventilation (including ECMO) or die by Day 28 will be included.

The DMC may request efficacy data if they feel there is value and to confirm a reasonable benefit/risk profile for ongoing patients in the studies. Further details are given in the DMC Charter.

### **6.16.2. Sample Size Re-Estimation**

This section provides an overview of design parameters for this sample size adaptive trial. It includes a detailed description of the unblinded sample size procedure and associated formulas for executing the design.

For purposes of sample size re-estimation, the overall  $\alpha$  will be split such that 90% is allocated to Population 1 ( $\alpha_1$ ).

The proposed sample size re-estimation may result in overall sample sizes from approximately 1400 patients to 1700 patients.

#### **6.16.2.1. Execution Details**

An interim analysis will be performed when approximately 1000 patients have randomized in the trial and had the opportunity to contribute data to the primary endpoint (i.e., had the opportunity to complete the study or discontinued). This analysis will be used to determine the final sample size of the trial, in accordance with adaptive SSR methodology described in Mehta and Pocock (2011). Discontinuing the study due to safety concerns at the interim is also possible. Due to the uncertainty in enrollment projections, the exact timing of the interim may occur at a sample size smaller or larger than the planned number of 1000 patients.

At the interim analysis, the conditional power (CP) for statistical significance of the primary endpoint will be calculated for each of the two population separately using the CP formula as given in Mehta and Pocock (2011) for each dose-placebo comparison. The maximum of the two conditional powers will be considered. This CP could fall into one of the three zones: “Unfavorable” ( $CP < 30\%$ ), “Promising” ( $30\% \leq CP < 90\%$ ), and “Favorable” ( $CP \geq 90\%$ ). Sample size will be increased if the maximum of two CPs falls in the promising zone but will remain at the minimum otherwise.

### 6.16.2.2. Calculation of Conditional Power at Interim

Table KHAA.6.13 defines the values that are needed for the conditional power calculation at interim analysis.

**Table KHAA.6.13. Defining the Values for the Conditional Power Calculation**

Quantity	Input Value or Derivation/Calculation
$z_1$	This is the chi-square test statistic for testing difference between of baricitinib versus placebo for the primary efficacy analysis conducted using only patients included in the interim analysis .
$n_1$	This is the planned total number of randomized patients included in the interim analysis including both treatment groups. The interim is scheduled to occur when approximately 71% of randomized patients have had the opportunity to complete the treatment phase at $n_1 = 1000$ for Population 1. Due to the uncertainty in enrollment projections, the exact timing of the interim may occur at a sample size smaller or larger than the planned number of 1000 patients for Population 1. For Population 2, $n_1$ will be the number of patients observed at the time of the interim analysis in Population 2
$n_2$	This is the increment from $n_1$ for the total number of patients in both treatment groups should the study remain at the planned minimum sample size based on interim results. The planned minimum sample size is 1400 and if the interim occurs at the planned $n_1 = 1000$ , the increment needed to get to 1400 patients is $n_2 = 400$ for Population 1. For Population 2, the proportion of patients $p$ not on dexamethasone or other systemic corticosteroids will be estimated from the available data for patients requiring supplemental oxygen at baseline. $n_2$ for Population 2 will then be estimated by multiplying $n_2$ for the overall population by the observed proportion, i.e., ( $n_2$ for Population 2) = ( $n_2$ for Population 1) $\times p$

As provided in Mehta and Pocock (2011), the conditional power for the primary efficacy analysis is given by

$$CP(z_1, n_2) = 1 - \Phi\left(\frac{z_\alpha \sqrt{n_1 + n_2} - z_1 \sqrt{n_1}}{\sqrt{n_2}} - \frac{z_1 \sqrt{n_2}}{\sqrt{n_1}}\right)$$

where  $\Phi()$  is the cumulative distribution function of a standard normal variable. The CP will be calculated for Population 1 and for Population 2 with the prespecified split type-I errors  $\alpha_1$  and  $\alpha_2$  respectively. Note that this conditional power calculation assumes that the data post-interim follows a distribution with an effect size equal to the effect size observed at interim. The preceding conditional power formula is written in terms of the test statistic for the baricitinib versus placebo dose comparison.

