### 6.11.1. Primary Outcome and Methodology

The primary comparison of interest is the proportion of patients who die or require non-invasive ventilation/high-flow oxygen or invasive mechanical ventilation (including ECMO) by Day 28. The primary comparison will be performed on two different populations:

- Population 1 – all randomized patients
- Population 2 – patients who, at baseline, require oxygen supplementation and are not receiving dexamethasone or other systemic corticosteroids for the primary study condition.

Patients on non-invasive ventilation/high-flow oxygen at baseline will be counted toward this endpoint if they progressed to invasive mechanical ventilation. Treatment comparisons between baricitinib 4-mg QD + background therapy and placebo + background therapy will be made using logistic regression with baseline stratification factors and treatment group in the model.

- Pr.V: Proportion of patients who died or require non-invasive ventilation/high-flow oxygen or invasive mechanical ventilation (including ECMO) by Day 28. For patients who start with ventilation at baseline, the patients need to be worsening in symptom (at least 1-point worsening in NIAID-OS) to be counted.

For the primary comparison involving two different populations, the alpha will be split between the two populations such that 99% of alpha is assigned to Population 1 and the rest to Population 2. The primary endpoint will be met if any one or both of these two populations show a significant treatment effect.

If the sample size is increased as a result of the interim analysis, the Cui, Hung, and Wang (CHW) procedure (Cui et al. 1999) will be applied to the primary endpoints for the two populations and the secondary endpoints to control the type I error at a one-sided  $\alpha=0.025$  significance level. The CHW method ensures strong control of type I error when the sample size is increased in a data dependent manner. Details about the CHW statistics are provided in Section 6.16.2.4.

If the sample size is increased as a result of the interim analysis, an unadjusted point estimate for both of the primary efficacy analysis will be calculated and reported. A median unbiased point estimate and a stage-wise adjusted confidence interval for the primary efficacy analysis will be calculated and reported based on the approach described by Brannath and colleagues (Brannath et al. 2009) to assess sensitivity of the point estimate.

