### 6.16.2.3. New Sample Size Calculation

If the sample size is increased as a result of the interim analysis, in which the maximum conditional power of the two populations is in the “promising zone,” the sample size will be increased for both treatment groups to maintain the 1:1 ratio. The formula for the updated sample size to maintain a targeted conditional power is provided in Mehta and Pocock (2011) and is given below. The formula below represents the recommended updated total sample size to maintain 90% conditional power. The value  $z_1$  in the formula is the interim test statistic corresponding to the population with the maximum conditional power.

$$N_{new} = n_1 + \left[ \frac{n_1}{z_1^2} \right] \left[ \frac{z_{\alpha} \sqrt{(n_1+n_2)} - z_1 \sqrt{n_1}}{\sqrt{n_2}} + (\Phi^{-1}(0.90)) \right]^2$$

If the maximum conditional power is observed corresponding to Population 2, then the increment in sample size obtained from the formula will be divided by the proportion of patients not on dexamethasone or other systemic corticosteroids obtained from the data as described before to get the increment in the overall sample size.

If the results of the interim analysis suggest an increase in the sample size, the final sample size will be the minimum of  $N_{new}$  and 1700.

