### 6.16.2.4. Calculation of CHW Statistics

The final CHW test statistic for the primary efficacy analysis (at the completion of the treatment phase after the sample size re-estimation) can be written as a weighted combination of the independent increments comprising the interim Wald test statistic and the post-interim Wald test statistic (Cui et al. 1999; Mehta and Pocock 2011):

$$z_{chw} = \frac{\sqrt{n_1}}{\sqrt{n_1+n_2}} z_1 + \frac{\sqrt{n_2}}{\sqrt{n_1+n_2}} z_2$$

Here  $z_1$  is the test statistic for the test conducted using the interim population and  $z_2$  is the test statistic for the test conducted using only the set of patients included in the post-interim assessment.

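### SAP Table KHAA.6.13 defines the interim z1 as a chi-square statistic, but the conditional-power, new-sample-size and CHW formulas need a signed standard normal value; neither the square root nor the sign is stated.

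*SAP*

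**What the plan says.** Table KHAA.6.13 in SAP 6.16.2.2 lists the inputs to the interim conditional-power (CP) calculation. For z1 it says: "This is the chi-square test statistic for testing difference between of baricitinib versus placebo for the primary efficacy analysis", restricted to patients in the interim analysis. The CP formula below the table sets z1 against z_alpha inside the standard normal distribution function. The text adds that the calculation "assumes that the data post-interim follows a distribution with an effect size equal to the effect size observed at interim", and that the formula refers to the comparison of baricitinib with placebo.

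SAP 6.16.2.3 uses the same symbol in the formula for the new total; there z1 "is the interim test statistic corresponding to the population with the maximum conditional power".

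SAP 6.16.2.4 builds the final CHW statistic as a weighted sum of "the interim Wald test statistic and the post-interim Wald test statistic". It then says only that z1 "is the test statistic for the test conducted using the interim population".

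The decision rule in SAP 6.16.2.1 is: "Sample size will be increased if the maximum of two CPs falls in the promising zone", meaning CP of at least 30% and below 90%. SAP 6.16.1 words this more softly: "the DMC may recommend increasing the sample size if the criteria for increase are met". SAP 6.11.1 applies CHW to the primary and secondary endpoints "to control the type I error at a one-sided" level of 0.025. It waives CHW if the recommended larger number had already been enrolled before the interim was completed.

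No section tells the programmer to take a square root, and none says which sign means benefit.

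**The concern.** A one-degree-of-freedom chi-square is the square of a standard normal z. It is on a different scale and has lost its direction. All three formulas use z1 linearly next to standard normal quantities, and the confirmatory test is one-sided, so both scale and sign matter. The endpoint is an unfavourable proportion, so a baricitinib-minus-placebo statistic is negative when the drug works. The wording about comparing baricitinib with placebo therefore does not settle the sign.

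Two things depend on this input. The first is the zone that decides between 1400 and up to 1700 patients. The second is the CHW statistic, the confirmatory test after an increase, which reuses the symbol without redefining it. The word Wald in 6.16.2.4 does not resolve the matter, because a Wald statistic can be reported as z or as chi-square.

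**Working it through.** **Inputs.** n1 = 1000, minimum total 1400 and n2 = 400 (Table KHAA.6.13); zone 30% to 90% (6.16.2.1); target CP 90% and cap 1700 (6.16.2.3); one-sided 0.025 overall (6.6); 90% weight on Population 1 for re-estimation (6.16.2) and 99% at the final analysis (6.6, 6.11.1). The simple splits are 0.9 × 0.025 = 0.0225 (z_alpha = 2.0047) and 0.99 × 0.025 = 0.02475 (critical value 1.964). The 25% placebo rate is from protocol 9.2; 20% on baricitinib is an assumption.

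**The plan's own figures.** 1000/1400 = 71.4% and 1400 − 1000 = 400, as stated. The SAP gives no worked CP or new sample size.

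**The formulas are coherent for a signed z.** Take z1 = 1.90.
- First term: (2.0047√1400 − 1.90√1000)/√400 = (75.007 − 60.083)/20 = 0.746.
- CP = 1 − Φ(0.746 − 1.90√0.4) = 1 − Φ(0.746 − 1.202) = 0.676.
- N_new = 1000 + (1000/3.61)(0.746 + 1.282)² = 2139 before the cap.
- Putting the increment of 1139 back, with the planned n2 kept in the first term as the CHW weights require, gives CP 0.900. At the 1700 cap CP is 0.80.

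With the chi-square value 3.61 as z1, CP exceeds 0.999 and N_new is 1035, below the 1400 minimum.

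**Promising zone.** The CP argument is 3.750 − z1(1.581 + 0.632) = 3.750 − 2.214 z1.
- CP = 30%: z1 = (3.750 − 0.524)/2.214 = 1.457.
- CP = 90%: z1 = (3.750 + 1.282)/2.214 = 2.273.
- If z1 is a chi-square, these limits apply to z², so the zone is |z| from √1.457 = 1.207 to √2.273 = 1.508, in either direction.

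With a parametric alpha1 of 0.0236 (if Population 2 is 40%), the zones are 1.440 to 2.255 and 1.200 to 1.502, so the conclusion is unchanged.

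| Signed z at the look | CP, signed z | CP, chi-square as labelled |
|---|---|---|
| 1.30 | 19.1% (unfavourable) | 49.6% (promising) |
| 1.75 | 54.9% (promising) | 99.9% (favourable, no increase) |
| −1.50 (harm) | about 0% | 89.1% (promising) |

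Reversing the sign also matters. At 25% versus 20%, z is about 1.89 and CP 67.0% if benefit is positive, but CP is about 0% if it is coded baricitinib minus placebo.

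**Chance of a promising call and power at 25% versus 20%.** The interim mean z is 0.05/√[(0.25×0.75 + 0.20×0.80)/500] = 1.897. The probability of falling in the zone is 31.6% with a signed z and 10.4% with the chi-square. Testing finally at 0.02475 with a signed z in CHW, power is 64.5% under the intended rule, 62.4% under the literal rule and 61.0% with no re-estimation.

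**Type I error.** The CHW statistic is √(1000/1400) z1 + √(400/1400) z2 = 0.845 z1 + 0.535 z2. For a signed z1 of 2.0, rejection needs z2 above (1.964 − 1.690)/0.535 = 0.51. If 4.0 is entered instead, z2 need only exceed (1.964 − 3.381)/0.535 = −2.65. Integrating over the null distribution of the interim z, at nominal 2.475%, with chi-square values entering only when N is increased:

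| What enters CHW | After a correctly coded look | After a literally coded look |
|---|---|---|
| Signed z1 and z2 | 2.475% | 2.475% |
| Chi-square z1, signed z2 | about 6.0% | about 4.4% |
| Chi-square z1 and z2 | about 7.1% | about 6.0% |

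**The case against.** The strongest reply is that no competent statistician would misread the section. The symbol z, z_alpha, the standard normal distribution function, the assumption that the observed effect continues, the word Wald and one-sided testing at 0.025 all point to a signed z. The formulas and the stated figures are right, so this is a slip in one label. The DMC charter, to which SAP 6.16.1 defers, and the cited methods papers may state the convention; neither is available here. The look took place in January 2021 (SAP 5.2), and the version of the SAP in force then is not supplied, so editing Version 4 cannot change that decision. Exposure is also limited: the DMC may only recommend an increase, and CHW applies only if N is increased and the waiver in 6.11.1 does not apply.

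Most of this stands, and it keeps the point minor. It does not correct the only explicit definition of z1 in the SAP. SAP 6.16.2 presents itself as a detailed account of the procedure and the formulas for carrying it out. Version 4 edited that section and left a definition under which the stated rule gives the wrong zone.

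A reader might infer that the interim was calculated wrongly or that the trial's type I error is inflated. The documents support neither. Nothing shows literal coding, and with a signed z in CHW the error rate is nominal whichever zone was used to choose N. The 4.4% to 7.1% figures need a second mistake, at the final analysis.

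**Conclusion.** Minor, and wrong as written. The stated input does not fit the three formulas that use it, the square root and sign are missing, and two labels are used for one quantity. A signed z is clearly the likely intent.

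Conditional on literal coding, the consequence for the decision is a zone that is displaced and blind to direction. The loss of power at 25% versus 20% is about two percentage points (64.5% to 62.4%). Type I error is at risk only if a chi-square value itself is put into CHW.

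These sizes assume the planned n1 and n2, Population 1 alone (the rule takes the larger CP of two populations), simple alpha splits, and the assumed event rates. Other choices change the figures, but not the finding that the label and the formulas disagree.

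**What to change.** 1. First, have the independent statistics group record in a file note which statistic, model and sign were used at the January 2021 look. Relabelling z1 as Wald without this step could misdescribe a look that used a Pearson chi-square.
2. Then define z1 and z2 in SAP 6.16.2.2 to 6.16.2.4 as the signed standard normal statistic from that same test: the signed square root of the one-degree-of-freedom chi-square, positive when baricitinib has fewer events. Use one label throughout.
3. If CHW applies (N increased and the waiver in 6.11.1 not triggered), enter that signed value for each stage, never the chi-square itself.

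The cost is one sentence in the table, matching wording in 6.16.2.3 and 6.16.2.4, and one file note. No patients are needed, and no reanalysis if a signed z was used.

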### 6.16.2.3. New Sample Size Calculation

If the sample size is increased as a result of the interim analysis, in which the maximum conditional power of the two populations is in the “promising zone,” the sample size will be increased for both treatment groups to maintain the 1:1 ratio. The formula for the updated sample size to maintain a targeted conditional power is provided in Mehta and Pocock (2011) and is given below. The formula below represents the recommended updated total sample size to maintain 90% conditional power. The value  $z_1$  in the formula is the interim test statistic corresponding to the population with the maximum conditional power.

$$N_{new} = n_1 + \left[ \frac{n_1}{z_1^2} \right] \left[ \frac{z_{\alpha} \sqrt{(n_1+n_2)} - z_1 \sqrt{n_1}}{\sqrt{n_2}} + (\Phi^{-1}(0.90)) \right]^2$$

If the maximum conditional power is observed corresponding to Population 2, then the increment in sample size obtained from the formula will be divided by the proportion of patients not on dexamethasone or other systemic corticosteroids obtained from the data as described before to get the increment in the overall sample size.

If the results of the interim analysis suggest an increase in the sample size, the final sample size will be the minimum of  $N_{new}$  and 1700.

### 6.16.2.4. Calculation of CHW Statistics

The final CHW test statistic for the primary efficacy analysis (at the completion of the treatment phase after the sample size re-estimation) can be written as a weighted combination of the independent increments comprising the interim Wald test statistic and the post-interim Wald test statistic (Cui et al. 1999; Mehta and Pocock 2011):

$$z_{chw} = \frac{\sqrt{n_1}}{\sqrt{n_1+n_2}} z_1 + \frac{\sqrt{n_2}}{\sqrt{n_1+n_2}} z_2$$

Here  $z_1$  is the test statistic for the test conducted using the interim population and  $z_2$  is the test statistic for the test conducted using only the set of patients included in the post-interim assessment.

